### Arm/Group Title \*

Intervention group= Group A

Controlled group= Group B

### Arm/Group Description \*§

Those 110 participants come from two classes in the same grade. One will be randomly allocated as the intervention group, the other will be control group.

**Overall Number of Baseline Participants \***

There will be 110 participants initiating the intervention.

**Baseline Measure Information \***

A group of demographic characteristics will be measured in the study, including gender, age, income per month of the family, etc.

**Baseline Measure Title \***

- Age \* : Continuous(years)
- Gender \* : Female, Male
- Income per month: Categorical:
  - <=1000 RMB
  - >1000 and <2000 RMB
  - >=2000 RMB
- The reason of being a nurse: nominal:
  - Out of interest
  - Advice from parents
  - Others

**Measure Type \***

- Count of Participants: Gender
- Mean: Age
- Number: Income per month, The reason of being a nurse

**Measure of Dispersion \***

- Standard Deviation
- Inter-Quartile Range
- Full Range

**Baseline Measure Data \***

The value(s) for each baseline measure, for each group and overall cannot obtain right now since the study has not been started.

**3. Outcome Measures****Outcome Measure Information \***

A questionnaire will be used during each measurement, including several scales in it.

**Outcome Measure Type \***

- Primary and secondary

**Outcome Measure Title \***

- Professional identity: professional identity in recent one week measured by Chinese Profession identity scale for nursing student. It is a self-reported scale by adding up 17 items and the total score ranges from 17-85, with higher score reflects higher professional identity.
- Career self-efficacy: career self-efficacy in recent one week measured by Chinese career self-efficacy scale for nursing student. It is a self-reported scale by adding up 27 items and the total score ranges from 27-135, with higher score reflects higher career self-efficacy.
- Stress: a reflection of one's perceived stress in recent month measured by the subscale from the Depression, Anxiety, and Stress Scale (DASS-21). It is a self-reported scale, with 7 items in the stress subscale scoring from 0-21. The higher score, the higher stress.
- Resilience: resilience in recent one week measured by Chinese version of Connor-Davidson Resilience Scale-10. It is a self-reported scale by adding up 10 items and the total score ranges from 0-40, with higher score reflects higher resilience.
- General rating: several descriptive question to gather the feedback of the intervention.

**Outcome Measure unit \***

The professional identity, career self-efficacy, stress, and resilience are measured by scales with no unit.

**Outcome Measure Time Frame \***

There will be two measurements, before the intervention and immediately after intervention. They are defined as T0, T1.

**Analysis Population Information****Overall Number of Participants Analyzed \***

There will be 110 participants totally enrolled in the study.

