### Started \*

There will be 110 participants initiating the intervention.

Those 110 participants come from two classes in the same grade. One will be randomly allocated as the intervention group, the other will be control group.

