### Completed \*

We will do follow-up post intervention, and the number in the follow-up will be recorded.

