### Reason Not Completed Type [\*]

We will record the exact reason (Adverse Event) why participants do not complete the study. The reason may be not interested, lack of efficacy, lost to follow-up, withdrawal by subject or others.

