**Method [\*]**

- ANOVA
- Chi-Squared
- t-Test, 2-Sided
- Other: repeated measurement of variance analysis within different measurements among different groups

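### No analysis set or missing-T1 rule is stated, so the listed tests default to a completers-only comparison although non-completion, including for lack of efficacy, is foreseen

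*Combined protocol and SAP*

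**What the plan says.** In section 3, the field for the number of participants analysed reads in full: "There will be 110 participants totally enrolled in the study". The same total appears in section 1 under Started: "There will be 110 participants initiating the intervention". The Pre-assignment Details table splits it 55 and 55, and allocation is by whole class: "One will be randomly allocated as the intervention group, the other will be control group".

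The plan allows for students not finishing. Under Reason Not Completed Type: "We will record the exact reason (Adverse Event) why participants do not complete the study", followed by "The reason may be not interested, lack of efficacy, lost to follow-up, withdrawal by subject or others". Under Completed: "We will do follow-up post intervention, and the number in the follow-up will be recorded". The Pre-assignment Details table also has a follow-up row in which numbers are to be recorded.

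On timing: "There will be two measurements, before the intervention and immediately after intervention". The Estimation Parameter is a mean difference in final values. The Method list gives ANOVA, chi-squared, a two-sided t-test and "Other: repeated measurement of variance analysis within different measurements among different groups".

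No section names an analysis set, a method for missing T1 scores, a drop-out allowance or a sensitivity analysis.

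**The concern.** There is only one post-baseline score. A student without it contributes nothing to a t-test or ANOVA of T1, and standard repeated-measures ANOVA removes that student's T0 as well. Since the plan is silent, the people analysed will be whoever returned T1, while the field that should define them shows the enrolled total.

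This matters because one listed reason for leaving, lack of efficacy, is related to the outcome. The arms also ask different things of students: five weeks of online group sessions against messages forwarded by the researchers. Loss could therefore differ between arms in amount, in kind, or both, and the completers' difference would then not estimate the difference between the groups as allocated.

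**Working it through.** **The plan's own figure.** 55 + 55 = 110. This is the enrolled total. The plan gives no effect size, SD, power or drop-out rate, so nothing further can be reproduced. All rates, gaps and correlations below are assumptions.

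**Would all 110 have T1?** If each student independently misses T1 with probability d, the chance of no loss is (1 − d)^110:
- d = 1%: 0.99^110 = 33%
- d = 5%: 0.95^110 = 0.35%

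The number with T1 would be 110 × (1 − d): 99 at 10% loss and 88 at 20%.

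**Shift from outcome-related loss.** In one arm, let a fraction d lack T1 and let their unseen mean lie g SD below the completers' mean. The full-arm mean is (1 − d) × completers + d × leavers, so the completers' mean is too high by d × g. For the difference, intervention minus control:

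bias = d_A × g_A − d_B × g_B

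where A is the intervention arm and B the control arm.

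| Assumed loss | g = 0.3 SD | g = 0.5 SD |
|---|---|---|
| 20% in A only | 0.2 × 0.3 = +0.06 | 0.2 × 0.5 = +0.10 |
| 30% in A only | 0.3 × 0.3 = +0.09 | 0.3 × 0.5 = +0.15 |
| 20% in B only | −0.06 | −0.10 |
| 20% in both, same g | 0 | 0 |

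Signs are for scales where higher is better. For stress, where higher is worse, they reverse.

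As an outer bound, suppose there is no true effect, scores are normal, and arm A loses exactly its lowest scorers. The shift is φ(z_d)/(1 − d): 0.20 SD at 10% loss and 0.35 SD at 20%.

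**Does the choice of test matter?** Suppose loss in arm A depends on T0 only, leavers are g0 SD below completers at T0, the T0–T1 correlation is ρ with equal variances, and there is no true effect.
- Difference in final values: shifted by d × ρ × g0.
- Group-by-time contrast, which with two time points is the difference in change: shifted by −d × (1 − ρ) × g0.
- T0-adjusted difference: no shift if T1 is linear in T0.

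With d = 0.2, g0 = 0.5 and ρ = 0.6, these are 0.2 × 0.6 × 0.5 = +0.06 SD, −0.2 × 0.4 × 0.5 = −0.04 SD, and 0. A simulation with these values gave +0.059, −0.040 and −0.001.

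So adjusting for T0 removes the part of the loss that T0 explains. It does not remove loss that depends on the unseen T1 score, which is what leaving for lack of efficacy may produce.

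**The case against.** A reader might infer that the plan promises 110 analysed and so contradicts itself. The text does not go that far. It says enrolled, in a results template completed before the study began, and the participant table marks 110 as anticipatory. The field is better read as leaving the analysis set undefined. Nor can the number be called unattainable: 110 would be reached if nobody missed T1.

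It is also tempting to say that drop-out is expected and will favour the intervention. The plan lists what reasons may be, gives no rate, and ties no reason to an arm. Students receiving messages could equally leave for lack of efficacy, and equal loss with equal gaps gives zero net bias.

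Two further points stand. The plan already records follow-up numbers and reasons for non-completion, so attrition would not be hidden. And nothing restricts the T1 questionnaire to students who finish the sessions. The completers-only result is the default of the listed tests, not something the plan states.

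These points limit the claim without removing it. Recording how many are missing does not say how they are analysed, and permitting T1 from non-attenders does not commit the investigators to seeking it.

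**Conclusion.** The concern holds in a conditional form. The plan foresees non-completion, depends on a single post-baseline score, lists tests that in standard form drop students without it, and states no analysis set or missing-data method. If T1 loss is related to outcome and differs by arm, the estimated difference is biased in a direction that cannot be known in advance. Under the assumed 20% loss in one arm only and a gap of 0.3 to 0.5 SD, the shift is 0.06 to 0.10 SD. The documents support neither the rate nor the gap.

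Loss of T1 also costs precision. No power figure is given here, because calculations that treat the 110 students as independent ignore the allocation of one whole class to each arm and would overstate the trial's power.

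This should be changed before analysis. It affects the estimate and whom it describes.

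**What to change.** 1. Send the T1 questionnaire to every allocated student, including those who stop attending sessions or reading messages. This comes first because it is the only step that recovers the missing outcomes.
2. Analyse all students in the arm assigned, with a T0-adjusted analysis in place of repeated-measures ANOVA or an unadjusted t-test. ANCOVA of T1 on T0 is the simplest choice. A mixed model with T0 and T1 as outcomes also keeps students who have T0 only. Do not force a common T0 mean: with one class per arm, equal starting means cannot be presumed.
3. Add a sensitivity analysis that fills in missing T1 scores and then shifts them unfavourably by stated amounts, for example 0.3 and 0.5 SD, with the sign reversed for stress. State which arm or arms are shifted, and include the intervention arm alone. Step 2 does not correct loss that depends on the unseen T1 score, so this step is needed as well.
4. Restate the analysed-number field as 110 allocated, with the number having T1 reported by arm.

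The cost is plan wording, a few extra online reminders and some additional analysis. The estimate may be smaller once non-attenders are kept.

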**Outcome Measure Data Table****Measure Type \***

- Mean

**Measure of Dispersion/Precision \***

- Standard Deviation

**Outcome Data \***

The measurement value(s) for each outcome measure cannot obtain right now since the study has not been started.

**Statistical Analysis Overview****Comparison Group Selection [\*]**

We will compare two groups' data.

**Type of Statistical Test [\*]**

- Superiority
- Other (descriptive analysis)

**P-Value [\*]**

P-Value will be set at 0.05.

**Method [\*]**

- ANOVA
- Chi-Squared
- t-Test, 2-Sided
- Other: repeated measurement of variance analysis within different measurements among different groups

**Estimation Parameter [\*]**

- Mean Difference (Final Values)

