## 2. Baseline Characteristics

### Arm/Group Information \*

Chi-square test will be applied to figure out the difference of enumeration data between two groups. ANOVA will be applied to test the difference of measurement data between two groups. F values and  $\chi^2$  values will be displayed to show the baseline data are no different in two groups.

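### The planned effect estimate ignores the T0 scores and does not match the listed repeated-measures test; no primary analysis is named, and baseline tests are used as proof of balance

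*Combined protocol and SAP*

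**What the plan says.** - **Data collected.** Outcome Measure Information: "A questionnaire will be used during each measurement, including several scales in it". Outcome Measure Time Frame: "There will be two measurements, before the intervention and immediately after intervention. They are defined as T0, T1". The four scored scales (professional identity, career self-efficacy, stress, resilience) are therefore available at both times.
- **Estimate.** Estimation Parameter has a single entry: "Mean Difference (Final Values". No covariate is named in any section.
- **Tests.** Method lists ANOVA, chi-squared, a two-sided t-test and "repeated measurement of variance analysis within different measurements among different groups". None is tied to an outcome or an estimate, and none is called primary. The significance level is 0.05.
- **Baseline.** Arm/Group Information in section 2 plans chi-square tests and ANOVA, whose "values will be displayed to show the baseline data are no different in two groups". Baseline Measure Information describes the variables thus: "A group of demographic characteristics will be measured in the study, including gender, age, income per month of the family, etc". The list that follows it does not name the T0 scale scores.
- **Allocation.** The 110 students come from two classes. "One will be randomly allocated as the intervention group, the other will be control group".

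**The concern.** A difference in final values leaves out the T0 score, usually the strongest available predictor of the T1 score. It is less precise than it needs to be, and any T0 gap between the classes passes wholly or partly into the reported effect. Because each arm is one intact class, such a gap is a realistic risk.

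The listed repeated-measures ANOVA does use T0, but it answers a different question from the named estimate. A report could pair a T1 mean difference with a p-value for change. Since no analysis is named as primary, the choice can be made after the data are seen.

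The planned baseline tests could then be read as clearing the groups of imbalance, which they cannot do at this sample size.

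**Working it through.** **Inputs from the plan:** 110 students, 55 per group; two measurements; alpha 0.05, two-sided (the t-test is listed as 2-sided).

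**Assumptions, because the plan gives no values:** T0-T1 correlation rho = 0.3, 0.5 or 0.7, with equal SDs at T0 and T1; an illustrative true effect of 0.4 SD; an illustrative baseline gap of 0.3 SD; ICC 0.01 to 0.05. The plan gives no effect size, SD or power, so its figure of 110 cannot be reproduced.

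**Step 1. Does the repeated-measures test match the estimate?** With two times, the group-by-time F equals the squared t for change scores. In a simulated data set of 55 + 55, the group-by-time F was 2.469 and the squared t for change was also 2.469. The squared t for T1 values was 3.218, and the group main effect, which averages T0 and T1, had F = 1.596. Neither of the two terms involving group is the test of the final-value difference.

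**Step 2. Precision.** In SD units, SE(final) = sqrt(2/55) = 0.191. The variance relative to final values is 1 - rho² for ANCOVA and 2(1 - rho) for change. Power comes from the noncentral t with 108 df (107 for ANCOVA). The equivalent N for ANCOVA is 110/(1 - rho²).

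| | rho 0.3 | rho 0.5 | rho 0.7 |
|---|---|---|---|
| Relative variance, ANCOVA | 0.91 | 0.75 | 0.51 |
| Relative variance, change | 1.4 | 1.0 | 0.6 |
| Power at 0.4 SD, final values | 54.7% | 54.7% | 54.7% |
| Power at 0.4 SD, ANCOVA | 58.7% | 67.0% | 82.9% |
| Power at 0.4 SD, change | 42.0% | 54.7% | 76.5% |
| Equivalent N, ANCOVA | 120.9 | 146.7 | 215.7 |

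At an assumed 0.5 SD effect (normal approximation), final values give 74.6% and ANCOVA 78.5%, 85.7% and 95.7%.

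**Step 3. How much of a 0.3 SD baseline gap remains in the effect?**

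A chance gap regresses towards the mean. It leaves rho × 0.3 in final values, 0 in ANCOVA and -(1 - rho) × 0.3 in change. A stable class gap is present at both times. It leaves 0.3 in final values, (1 - rho) × 0.3 in ANCOVA and 0 in change.

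| Gap left (SD), rho 0.3 / 0.5 / 0.7 | Final values | ANCOVA | Change |
|---|---|---|---|
| Chance gap | 0.09 / 0.15 / 0.21 | 0 / 0 / 0 | -0.21 / -0.15 / -0.09 |
| Stable gap | 0.30 / 0.30 / 0.30 | 0.21 / 0.15 / 0.09 | 0 / 0 / 0 |

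Simulation with 8,000 runs per case agreed within 0.005 SD. ANCOVA carries less than final values in both cases; change is free of the gap only when the gap is stable.

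**Step 4. Can a baseline test show balance?** With noncentrality 0.3/0.191 = 1.57, power to detect a true 0.3 SD gap is 34.5%, so the test misses it 65.5% of the time. An observed gap must exceed 0.378 SD to reach p < 0.05.

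**Step 5. Clustering.** SE = sqrt((2/55) × (1 + 54 × ICC)): 0.191 at ICC 0, 0.237 at 0.01, 0.275 at 0.02 and 0.367 at 0.05. An individual-level test run at a nominal 5% then has a true type I error of about 11% at ICC 0.01 and 31% at 0.05. The powers in Step 2 are therefore best cases.

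**The case against.** - **The estimate does match two of the listed tests.** A final-value difference is what the t-test and the one-way ANOVA examine. This stands: the mismatch is only with the repeated-measures test. The plan also does not say which repeated-measures term would be reported, so the harm is possible rather than certain. That silence is itself part of the problem.
- **The lack of adjustment is inferred.** No sentence rules out a covariate. That is true, but a final-value difference is by name a T1 comparison, and no covariate or model appears elsewhere to alter that reading.
- **ANCOVA is not the only defensible choice.** For a stable class gap, which the allocation makes plausible, the change contrast already on the list leaves nothing, while ANCOVA leaves 30% to 70% of the gap. This is a fair point and the reason to keep the change contrast as a named sensitivity analysis. ANCOVA still has the higher power at every rho used here, and it is the one that handles a chance gap.
- **The T0 scores may be among the variables tested.** The baseline description is open-ended, and F values in the plural suggest more than age. That is possible, but the plan does not say so, and a non-significant result would still not show balance.
- **The figures depend on assumed values.** They do. At rho 0.3 the gain at 0.4 SD is only 4 percentage points. Nor do the powers describe a valid test once between-class variation is present; they compare the analyses with one another and no more.

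**Conclusion.** The concern holds, as something the sponsor should change. The plan collects a T0 score on every scale and does not use it in the only estimate it names. The repeated-measures test it lists addresses a different contrast, and nothing fixes which analysis counts.

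The loss depends on rho, which the plan does not give. It runs from small (55% against 59% power at rho 0.3) to large (55% against 83% at rho 0.7) for an assumed 0.4 SD effect with independent participants. A 0.3 SD baseline gap leaves 0.09 to 0.30 SD in the planned estimate, depending on its nature and on rho; in ANCOVA it leaves 0 to 0.21 SD. That the estimate is incomplete, that the repeated-measures test differs from it, and that baseline tests cannot prove balance do not depend on these assumed values.

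The larger defect, one class per arm, is separate and remains whatever model is used.

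**What to change.** 1. **Method:** for each of the four scales, name as the primary analysis an ANCOVA of the T1 score on group, adjusted for the same scale's T0 score. Include no class term, because class and arm are the same thing.
2. **Estimation Parameter:** replace the final-value difference with the baseline-adjusted mean difference and its 95% CI.
3. **Method:** keep the group-by-time (change-score) contrast as a named sensitivity analysis, since it removes a stable class gap that ANCOVA removes only in part.
4. **Section 2, Arm/Group Information:** replace the tests offered as proof of balance with descriptive summaries or standardised differences, and include the four T0 scale scores.
5. **Section 5, Limitations and Caveats:** add that with one class per arm no adjustment can separate class from intervention, and that the CI and p-value ignore between-class variation.

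The cost is a change of wording and one degree of freedom per model; no new data are needed. Which scale is the primary outcome, and how multiplicity across the four is handled, must be settled separately.

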**4. Adverse Event Information****Time Frame \*§**

The intervention lasts around 35 days, with 5 times, and we will record the adverse event at each time.

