### Arm/Group Description \*§

**Intervention group:** Students will be intervened by an online 5-week professional identity group psychotherapy.

**Controlled group** will receive online messages of self-care knowledge forward by researchers.

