**Collection Approach for Table Default \*§**

- Systematic Assessment: The psychotherapist will routinely determine whether or not certain adverse events have occurred through regular investigator assessment during intervention and in each follow-up.
- Non-Systematic Assessment: Self-reporting by participants or occasional assessment by the psychotherapist.

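### Before T1, scheduled adverse-event recording follows a pattern described only for Group A, so the by-group table of non-serious events may rest on unequal ascertainment

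*Combined protocol and SAP*

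**What the plan says.** Section 4, Time Frame, ties recording to the occasions of the intervention, which lasts about 35 days: "with 5 times, and we will record the adverse event at each time". No arm is named.

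Section 4, Collection Approach, gives two routes. The systematic one is that "The psychotherapist will routinely determine whether or not certain adverse events have occurred", both while the intervention runs and at every follow-up. The non-systematic one is "Self-reporting by participants or occasional assessment by the psychotherapist". Neither is limited to an arm.

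Section 1, Arm/Group Description, sets out the contact in each arm. In Group A, "Students will be intervened by an online 5-week professional identity group psychotherapy". Group B "will receive online messages of self-care knowledge forward by researchers", with no number of occasions and no role for the psychotherapist.

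Section 4, Adverse Event Term, names psychological discomfort as the most likely event and plans two tables by group, one for serious and one for other events. Adverse Event Reporting Description defers further information until the study has finished.

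**The concern.** Recorded discomfort depends on how often people are asked and by whom. If one arm is asked at every session and the other only at the end, the two columns of the non-serious table measure different things. A surplus in Group A could then come from more frequent enquiry, yet a reader could take it as harm caused by the therapy. What is at stake is the interpretation of that descriptive comparison, not the efficacy result.

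**Working it through.** The plan states no adverse-event rate, detection probability or derived safety figure, so there is nothing to reproduce. The check compares the text by arm and then works out the direction.

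**1. Are the five occasions study-wide?** They are not the study's measurement points. Section 3, Outcome Measure Time Frame, says "There will be two measurements, before the intervention and immediately after intervention", that is, T0 and T1 only. They are occasions of the intervention. The length matches Group A's programme: 5 weeks × 7 days = 35 days. No five occasions are described for Group B.

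**2. Who is in contact with Group B before T1?** Only researchers forwarding messages. No contact between the psychotherapist and Group B is described during the 35 days.

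**3. What happens at T1?** Section 1, Milestone Title, defines T1 as the follow-up immediately after the intervention. The Collection Approach has the psychotherapist assess at follow-up without naming an arm. On a plain reading this gives both arms one check at T1.

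**4. Scheduled checks on this reading**, with 55 per arm and everyone attending:

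| | Before T1 | At T1 | Total |
|---|---|---|---|
| Group A | 55 × 5 = 275 | 55 | 330 |
| Group B | none described | 55 | 55 |

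Per person this is 5 + 1 = 6 against 1. If a common schedule is meant, both arms have 6 per person and 330 in total. These are counts of checks, not of events.

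**5. Direction at equal true risk.** Suppose that an event can be detected at each of m remaining checks, independently with probability p, and that it is self-reported with probability s in either arm. The chance that it is recorded is 1 − (1 − s)(1 − p)^m.

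- An event present by one of the five sessions and still detectable or recalled at T1 has m between 2 and 6 in Group A, and m = 1 in Group B. For p strictly between 0 and 1 and s below 1, the Group A value is larger.
- If the event has gone by T1 and is not recalled there, Group B has only s.
- An event arising after the last session has m = 1 in both arms, so there is no difference.
- The gap closes if detection at T1 is complete for everything since the start (p = 1 with persistence or full recall), if self-report is complete (s = 1), or if both arms share the schedule.

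The documents give neither p nor s, nor how long discomfort lasts. The argument therefore gives a direction and no size.

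**6. Is there symmetric information on distress?** Partly. Stress is defined as "perceived stress in recent month measured by the subscale from the Depression, Anxiety, and Stress Scale" and is taken in both arms at T0 and T1. Taking a month as 30 days, the T1 score looks back over 30/35 = 86% of the period. It is an outcome score, however, and not an adverse-event report.

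**The case against.** The strongest reply is that the sentence on timing names no arm. Section 1 (Started) and section 2 (Overall Number of Baseline Participants) both describe all 110 participants as starting the intervention, so one schedule for both arms may be intended. This stands as a possibility, and the finding depends on it. But no five occasions are described for Group B, so a common schedule would still have to be written down.

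Second, Group B is not left without any route. Self-report is open to everyone, and section 1 (Reason Not Completed Type) records reasons for stopping, including adverse events, in both arms. This stands too, and it would narrow the gap.

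A reader might go further and infer that Group B has no assessor and is never asked. The documents do not support that: the follow-up assessment is not restricted by arm. Section 3 says "A questionnaire will be used during each measurement, including several scales in it" and lists scales and feedback questions, with no adverse-event item. That passage describes outcome measurement, so its silence is weak evidence about safety collection.

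A reader might also infer that Group A's events would be over-recorded. Events found at sessions are real events; the problem is unequal ascertainment, which can equally be described as under-recording in Group B.

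**Conclusion.** The point holds as a minor one. Followed as written, the plan describes scheduled adverse-event checks before T1 only in a form that fits Group A, while Group B can be read as having one check at T1 plus self-report. At equal true risk, the by-group table of non-serious events would then tend to show more discomfort in Group A.

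This assumes that no common schedule is intended, and that neither the T1 check nor self-report captures everything that happened earlier. The size cannot be determined from the documents, and any risk ratio put on it would come wholly from assumed inputs.

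The consequence is limited. The table is descriptive, no adverse-event test is planned, efficacy is unaffected and Group A's own counts remain informative. It is still more than a missing detail, because the plan commits to a by-group display that the described collection would not make comparable.

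**What to change.** If a common schedule is already intended, state in section 4 who asks Group B, how and on which dates. Otherwise:

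- Put the same short self-report items on psychological discomfort, with the same recall window, to both arms. The minimum is one set at T1 covering the whole 35 days, placed after the outcome scales so that it cannot influence those answers. Preferably, also send the items online to both arms on the same five dates, each asking about the time since the last enquiry.
- Base the between-group reading of non-serious events on these common answers.
- Report session-observed or therapist-observed non-serious events separately, labelled as non-comparative. Checks at Group A's sessions continue unchanged.
- Keep serious adverse events from any source in the by-group table.

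The cost is a few online items. Both arms are already reached online, although Group B's message frequency is not stated, so the extra work there is uncertain but probably small. The T1-only version is lighter but relies on recall over 35 days. The five-date version adds slight questionnaire burden, some contact with controls and possibly minor reactivity in self-reported stress, which is a trial outcome. Identical items in both arms should make that reactivity largely shared, though this is not guaranteed.

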### Milestone Title [\*]

Before the intervention, we will measure the participants, and the stage is defined as T0.

We will do follow-up immediately after intervention, defined as T1.

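### Students who miss sessions or withdraw have no stated scheduled adverse-event check until T1, and none at all if they are lost before T1

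*Combined protocol and SAP*

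**What the plan says.** Four entries bear on how harms are collected.

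- Section 4, Time Frame, gives a duration of about 35 days with five occasions, and says "we will record the adverse event at each time".
- Section 4, Collection Approach for Table Default. The systematic part reads "The psychotherapist will routinely determine whether or not certain adverse events have occurred", and this is done "through regular investigator assessment during intervention and in each follow-up". The non-systematic part is "Self-reporting by participants or occasional assessment by the psychotherapist".
- Section 1, Milestone Title, defines the one follow-up: "We will do follow-up immediately after intervention, defined as T1".
- Section 1, Reason Not Completed Type: "We will record the exact reason (Adverse Event) why participants do not complete the study". It continues: "The reason may be not interested, lack of efficacy, lost to follow-up, withdrawal by subject or others".

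The Adverse Event Term entry in section 4 names psychological discomfort as the likeliest harm. It plans two tables by group, one for serious and one for other events. It gives no denominator and no rule for students who were not assessed.

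**The concern.** The scheduled checks coincide with the sessions, plus T1. In an online group psychotherapy, the harm the plan expects is also a plausible reason for not coming back. The chance of being asked about discomfort may therefore fall just when discomfort occurs.

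The safety summary for Group A is at stake. If events in students who stopped attending go unrecorded, the tables will make the intervention look better tolerated than it was. The reader could not see this, because nothing requires the number of students actually asked to be shown.

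**Working it through.** The plan states no figure to reproduce here, so the check sets the entries side by side.

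1. **Number of scheduled checks.** Five occasions (Time Frame) plus one follow-up (Collection Approach with Milestone Title) give 5 + 1 = 6 scheduled checks for a student who attends throughout.

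2. **Spacing.** 35 days / 5 occasions = 7 days, consistent with the five-week intervention in the Arm/Group Description. Even spacing is an assumption.

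3. **A student who stops after session k.** The session checks missed number 5 − k. For k = 2 that is 5 − 2 = 3 (sessions 3, 4 and 5). If reached at T1, the student has had sessions 1 and 2 plus T1, or 3 of 6 checks. If not reached at T1, the student has had 2 of 6, with none after leaving.

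4. **Delay if T1 is reached.** From session 2 to session 5 is 3 × 7 = 21 days, and T1 follows the intervention. T1 would then ask about discomfort roughly three weeks old, or somewhat older if T1 falls later than session 5.

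5. **Other routes for that student.** The plan itself classes self-report and occasional assessment as non-systematic. The reason for non-completion belongs to participant flow. No entry says that it feeds the adverse-event tables, and a student lost to follow-up may give no reason.

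6. **Group B.** This group receives online messages, and no sessions are described for it. The plan does not say how an assessment by the psychotherapist at five intervention occasions would work there, so whether the two groups are asked equally often is unclear.

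7. **Can the under-count be sized?** For a group of n students, let m stop early, let pL and pS be the proportions with an event among leavers and stayers, and let c be the share of leavers' events that is recorded. Assume that stayers' events are all recorded. Then
   - true count = m·pL + (n − m)·pS
   - recorded count = c·m·pL + (n − m)·pS
   - relative shortfall = (1 − c)·m·pL / [m·pL + (n − m)·pS]

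   The plan gives n = 55 per group and nothing for m, pL, pS or c. The shortfall is zero if nobody leaves, if leavers have no events, or if all their events are recorded (c = 1). Otherwise it is positive. The direction follows from the design, but the size does not.

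**The case against.** The strongest reply is that the plan has more safeguards than the Time Frame entry suggests. Systematic assessment extends to follow-up, so a student who skips sessions but is seen at T1 is assessed. The plan undertakes to record the exact reason for non-completion and names adverse event in that sentence. Self-report is open throughout. No entry makes attendance a condition of recording. If the check comes during or at the end of a session, distress arising within that session is caught there, and only later distress is missed. Leavers need not be distressed, since lack of interest and lack of efficacy are also listed as reasons.

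All of this stands, and it rules out three stronger readings that a reader might infer:

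- **That harms are assessed at sessions and nowhere else.** The follow-up wording in the Collection Approach contradicts this.
- **That students who were not assessed will be counted as free of events, over a denominator of 55.** The plan states neither. It is silent on both.
- **That the under-count can be put at some percentage.** Any such figure would rest on invented leaving and event rates. It would also be a ceiling if it gave no credit to T1, self-report or the recorded reason for leaving.

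The reply does not fill the gap itself. No entry provides for asking an absent or withdrawn student about harms before T1, or at all if T1 is missed. The non-systematic routes depend on the student volunteering or on chance contact.

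**Conclusion.** The point holds as a gap in ascertainment, and it is worth correcting because the remedy is cheap. Scheduled assessment rests on the five occasions and T1. A student who stops attending has no stated scheduled check in between, and none after leaving if lost before T1. The route from the reason for non-completion to the adverse-event tables, and the denominator of those tables, are undefined.

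Harm may be under-counted. That conclusion assumes that some leavers have events and that some of those events go unrecorded. It is plausible, but not documented, that discomfort leads students to stop. The size cannot be derived from the documents. The finding concerns the safety summary and does not touch the comparison of the questionnaire scores.

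**What to change.** - In section 4, Time Frame, state that the same short, private adverse-event question goes to every allocated student in both groups at each of the five scheduled dates and at T1, whether or not the student attended or has stopped, unless the student refuses further contact.
- State that any adverse event given as a reason for non-completion is also entered in the adverse-event tables.
- In those tables, show by group the number asked at each occasion, and show students not reached as unknown.

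The cost is one extra online item per date, some unanswered messages to students who have stopped, and extra rows in the tables. Recruitment notices, the intervention and the control messages are already online. The plan does not say how the questionnaire is delivered, so a private reply channel may have to be set up. Asking both groups the same question on the same dates would also settle how harms are collected in Group B.
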